### **10.2. Discontinuation of Treatment**

A patient should be discontinued from study treatment based on:

- Investigator discretion based on safety issues
- Progressive disease
- No response after the third course of therapy
- Any  $\geq$  grade 3 toxicity for > 2 weeks

### **10.3. Withdrawal From the Study**

A subject will be withdrawn from the study for any of the following reasons:

- Lost at follow-up
- Consent withdrawal
- Discontinuation of study treatment (final assessments will be obtained) if applicable

When a subject withdraws before completing the study, the reason for withdrawal is to be documented on the CRF and in the source document. Study drug assigned to the withdrawn subject may not be assigned to another subject.

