Primary testicular lymphomas (PTL) are very aggressive malignancies with poor prognosis. Five year survival ranged from 16% to 50% and median survival has been reported of only 12-24 months according to the different series of patients.2,8,7 The use of anthracycline-based chemotherapy has been associated with a 5-yr survival of 30-60% in different series, nevertheless there is a continuous relapse pattern with no evidence of plateau in the survival curve.9,10,11,12,7 Doxorubicin-containing regimens has allowed an improvement in the relapse-free survival comparing orchietomy  $\pm$  radiotherapy, however the advantage on survival time varied a lot among the different series published so far.13,11,7 In the largest series of patients reported so far by the IELSG (373 patients), the outcome of patients was extremely poor with an actuarial 5- and 10-years OS of 48% and 27% and an actuarial 5- and 10-years progression free survival of 48% and 33% respectively. The survival and PFS curves showed no clear evidence of a plateau, suggesting no cure for patients affecting by primary testicular lymphoma, even for those presenting with stage I/II (5 and 10 yrs OS in stage I 58% and 29%, stage II 46% and 29%7, respectively). The majority of patients with PTL relapse despite complete response to initial treatment. When radiation is given to the retroperitoneal lymph nodes, failures are systemic. Very few cases of in-field relapses have been reported. After chemotherapy both systemic and regional relapses are seen. Most relapses occurred in the first two years, but late relapses have also been described.14,7 One of the peculiar feature of PTL is a contralateral testis relapse occurring in 5-35% of the patients.5 In the retrospective series of 373 patients reported by IELSG, the commonest sites of relapse were: CNS (5 and 10-years risk of CNS relapse 20% and 35%) and contralateral testis (15% at 3 years, 40% at 15 years) occurring in patients not receiving prophylactic scrotal radiotherapy.7 Prophylactic irradiation of the contralateral testis has been proved to successfully prevent testicular recurrences in some studies.13,7 In the IELSG study prophylactic radiotherapy to contralateral testis was also associated with better PFS (5-year PFS 36% vs 70%) and OS (5-year OS 38% vs 66%). Moreover, CNS relapses are definitely more common than in other aggressive lymphomas and they have been reported up to 30% of the patients within 1-2 years from diagnosis. However, late relapse have also been described, sometimes as CNS relapse alone.12,11 The high rate of CNS recurrence is troublesome and has led to a recommendation for routine CNS prophylaxis. Although the use of prophylactic intrathecal chemotherapy has been advocated, its value is controversial because CNS relapses occur more frequently in brain parenchyma than in meninges and also in patients who had received intrathecal chemotherapy.6,7 The best strategy to prevent CNS relapse is still a matter of debate.

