# 9. STUDY EVALUATIONS

## 9.1. Study Procedures

### 9.1.1. Overview

Patients participation will include:

1. The pretreatment (screening) phase will be 30 days for all laboratory tests and radiographic imaging phase and up to 60 days for orchectomy and bone marrow evaluation.
2. The open label treatment phase will extend from the first day of the first course of R-CHOP to a maximum of 6 courses.
3. The consolidation phase will extend from the first day of the first course of Intermediate-dose MTX to the end of radiotherapy.
4. The follow-up phase will begin after the completion of the consolidation phase. Follow-up will continue until disease progression (PD), patient withdrawal, death or the study completion (expected to be 36 months from the date of the last patient's end of therapy).

Hematology results must be available and reviewed by the investigator to evaluate for possible hematological toxicity.

All subjects will be monitored for adverse events throughout the study and for 30 days after the end of treatment.

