**Overall survival** will be determined from the date of enrollment into the study to the date of death from any cause. Patients who have not died at the time of the final analysis will be censored at the date of the last contact.

**Event-free survival (time to treatment failure)** is measured from the time from study entry to any treatment failure including disease progression, or discontinuation of treatment for any reason (e.g. disease progression, toxicity, patient preference, initiation of new treatment without documented progression, or death). It may be useful in the evaluation of some therapies such as those that are highly toxic.

**Progression-free survival PFS** is defined as the time from entry onto a study until lymphoma progression or death as a result of any cause. PFS is the preferred end point in lymphoma involving incurable histologic subtypes clinical trials (e.g. follicular, other low-grade lymphoma, or mantle cell lymphoma). In studies in which failure to respond without progression is considered an indication for another therapy, such patients should be censored at that point for the progression analysis.

**Disease-Free Survival** is measured from the time of occurrence of disease-free state or attainment of a CR to disease recurrence or death as a result of lymphoma or acute toxicity of treatment. This definition may be complicated by deaths that occur during the follow-up period that are unrelated to the lymphoma, and there is controversy about whether such deaths should be considered as events or censored at the time of occurrence. Although it is often possible to identify those deaths related to the lymphoma, there is the potential for bias in the attribution of deaths.

**Lymphoma-Specific Survival** is defined as time from study entry to death as a result of lymphoma. This end point is potentially subject to bias because the exact cause of death is not always easy to ascertain. To minimize the risk of bias, the event should be recorded as death as a result of lymphoma, or as a result of toxicity from the drug. Death as a result of unknown causes should be attributed to the therapy.

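### Sections 10.3 and 9.1.1 end follow-up when treatment is stopped for toxicity, against 3.2, 9.1.7 and the PFS definition, so later progressions may go unobserved

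*Combined protocol and SAP*

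**What the plan says.** Section 10.2 lists grounds for stopping study treatment. Two of them do not involve progression or lack of response: "Investigator discretion based on safety issues", and toxicity at or above "grade 3 toxicity for > 2 weeks".

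Section 10.3 opens with "A subject will be withdrawn from the study for any of the following reasons" and includes in its list "Discontinuation of study treatment (final assessments will be obtained) if applicable". No exception is made for patients who stop without progression.

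Section 9.1.1, item 4, says: "Follow-up will continue until disease progression (PD), patient withdrawal, death or the study completion". The same item starts the follow-up phase once consolidation is complete.

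Two sections read differently. Section 3.2, item 4, has patients tracked for progression and survival up to study end, expected 36 months after the last patient finishes treatment, and asks for survival information up to 5 years. Section 9.1.7 moves all patients into follow-up after the end-of-treatment evaluation and closes follow-up only at death or progression. Neither mentions patients who stopped early.

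Section 9.3.1 says that PFS "is defined as the time from entry onto a study until lymphoma progression or death as a result of any cause". Its one censoring sentence for PFS covers patients who fail to respond without progressing. The EFS definition in the same section counts stopping treatment for any reason as an event. Section 2.2 makes 3-year PFS and 3-year EFS, set against historical treatment, a secondary objective.

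**The concern.** A patient in CR or PR whose treatment is stopped for toxicity has no PFS event. Under 10.3 this patient leaves the study after a final assessment, and under 9.1.1 follow-up ends there. A later relapse is then not looked for, although the PFS definition would count it. The plan does not say how PFS treats such a patient. The natural default is censoring at the last assessment.

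That matters because toxicity stops are central to a trial whose primary objective is safety and feasibility. A patient who stops early may also miss the methotrexate and the scrotal radiotherapy that come after R-CHOP. Section 1.1.1 associates radiotherapy with better PFS, and Sections 1.1.1 and 1.2 express the hope that methotrexate and intrathecal liposomal cytarabine will prevent CNS recurrence. If stopped patients do relapse more often, censoring them is informative and favours the regimen.

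**Working it through.** **The texts side by side, for a responder stopped for toxicity without progression**

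- 10.2: treatment stops.
- 10.3: the patient is withdrawn from the study, with final assessments where these apply.
- 9.1.1: withdrawal ends follow-up. Moreover, the follow-up phase starts only after consolidation, which this patient has not completed.
- 3.2 and 9.1.7: follow-up continues to study end, or to death or progression.
- 9.3.1: PFS needs progression or death. Stopping is not an event, and censoring at a toxicity stop is not mentioned.

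The first three statements and the fourth cannot both be applied to this patient.

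**Size, as illustration**

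The plan gives no figure to reproduce: the 35 patients come from expected accrual, and neither a toxicity-stop rate nor a risk after stopping is stated.

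Inputs: 5-year PFS of 70% with and 36% without prophylactic scrotal radiotherapy (Section 1.1.1, a non-randomised contrast in a retrospective series). Assumptions: exponential hazards; a share *d* stops at 3 months (0.25 years) and is censored there; the range for *d* is 10% to 30%.

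- Hazard if treatment continues: h1 = −ln(0.70)/5 = 0.0713 per year.
- Hazard after stopping, steep case: h0 = −ln(0.36)/5 = 0.2043 per year; ratio 0.2043/0.0713 = 2.86.
- Kaplan-Meier value with stoppers censored: exp(−3·h1) = 0.807.
- True value: S(3) = exp(−0.25·h1)·[(1−d)·exp(−2.75·h1) + d·exp(−2.75·h0)].
- Here exp(−0.25·h1) = 0.982, exp(−2.75·h1) = 0.822 and exp(−2.75·h0) = 0.570. The bias is therefore d × 0.982 × (0.822 − 0.570) = 0.247·d.
- With a hazard ratio of 2, exp(−2.75·2·h1) = 0.675, and the bias is d × 0.982 × (0.822 − 0.675) = 0.144·d.

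| Share stopping | True 3-year PFS, HR 2.86 | Estimate | Overstatement, HR 2.86 | Overstatement, HR 2 | HR 1 |
|---|---|---|---|---|---|
| 10% | 78.3% | 80.7% | 2.5 points | 1.4 points | 0 |
| 20% | 75.8% | 80.7% | 4.9 points | 2.9 points | 0 |
| 30% | 73.3% | 80.7% | 7.4 points | 4.3 points | 0 |

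**Cross-check with other anchors**

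Assume 3-year PFS of 0.70 or 0.78 in those who continue. The first borrows the alternative hypothesis of the earlier prospective study, the second its 3-year EFS. With stopping at month 4 and hazard ratios of 1.5 to 3, the overstatement runs from 0.8 points (PFS 0.78, 10% stopping, ratio 1.5) to 9.9 points (PFS 0.70, 30% stopping, ratio 3). For PFS 0.70, 20% stopping and ratio 2, the monthly hazard is −ln(0.70)/36 = 0.00991. The true value is exp(−4 × 0.00991) × [0.8·exp(−32 × 0.00991) + 0.2·exp(−64 × 0.00991)] = 0.961 × [0.8 × 0.728 + 0.2 × 0.530] = 0.662, against an estimate of 0.700. Unobserved events: 35 × 0.2 × 0.961 × (1 − 0.530) = about 3.2. Both models treat every later event as lost, which is the worst case where deaths are still recorded.

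**The case against.** The strongest reply is that the plan does not establish a loss of follow-up. Sections 3.2 and 9.1.7 can be read as keeping every patient under observation until death or progression. The 10.3 bullet ends with a qualifier that leaves room to keep following a patient. Section 10.1 defines study completion by the week 30 assessments, so withdrawal in Section 10 may refer to the treatment period and not to long-term follow-up. These points stand: this is an unreconciled conflict, not a settled rule. They do not remove the problem. Neither 3.2 nor 9.1.7 mentions patients who stopped early, the opening of 10.3 is mandatory, and follow-up that varies by site would be selective.

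A reader might go further and infer that the plan censors PFS at a toxicity stop and so reads 3-year PFS from patients who tolerated the program. The documents do not support that. No section states such censoring; stopped patients contribute up to the stop; and events during treatment count. Nor does any section link toxicity stops to later relapse. The 36% and 70% figures are a non-randomised association, Section 7 plans scrotal radiotherapy for all patients, and a stopped patient may still receive it.

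The effect is also modest beside sampling error. With 35 patients and PFS near 0.77, the 95% half-width is 1.96 × √(0.77 × 0.23/35) = about 14 points. PFS is secondary and has no test or threshold, EFS in the same objective already counts discontinuation, and deaths may still be captured through the 5-year survival requirement. All of this limits the consequence. Progression after a stop has no such safeguard, and imprecision does not excuse an avoidable systematic error.

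**Conclusion.** The point holds as a conflict in the text with a conditional effect on one secondary endpoint. Sections 10.3 and 9.1.1, followed as written, lose progressions that the PFS definition counts; Sections 3.2 and 9.1.7 imply that those progressions are collected. If they are lost, 3-year PFS is overstated only to the extent that patients stopped for toxicity have a higher later risk. Under the assumptions shown (10% to 30% stopping at month 3, exponential hazards, hazard ratio 2 to 2.9), the overstatement is about 1 to 7 points. At a hazard ratio of 1 there is lost information but no bias. Neither the stop rate nor the hazard ratio comes from observations on stopped patients, so these figures show an order of size and are not a forecast. An established upward bias cannot be claimed from the documents. EFS is not affected.

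**What to change.** In 10.3, separate stopping study treatment from withdrawal from the study. Amend 9.1.1, 3.2 and 9.1.7 in the same way, so that patients who stop without progression stay on the existing 9.1.7 visit and imaging schedule until progression, death, withdrawal of consent or study end. State in 9.3.1 that PFS includes all enrolled patients and is not censored at a toxicity stop.

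Deleting the 10.3 bullet alone is not enough: 9.1.1 would still end follow-up at withdrawal, and its follow-up phase would still start only after consolidation. The new wording should also be checked against 3.2, 6.1.1, 6.2.1 and 9.1.4, which withdraw or remove patients with progression or without response.

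The cost is a wording amendment, plus follow-up visits already in the schedule for the few patients who stop early. Progressions that are never assessed may not be recoverable later. The change concerns data collection and analysis only and takes no position on when treatment should be stopped.

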# 11. ADVERSE EVENT(AE) AND SERIOUS ADVERSE EVENT (SAE) REPORTING

Timely, accurate, and complete reporting and analysis of safety information from clinical studies are crucial for the protection of subjects and are mandated by regulatory agencies worldwide.

## 11.1. Definitions

### 11.1.1. Adverse Events definition and classification

#### **Adverse Event (AE)**

An adverse event is any untoward medical occurrence in a clinical study subject administered a pharmaceutical product. An adverse event does not necessarily have a causal relationship with the treatment. An adverse event can therefore be any unfavorable and unintended sign (including an abnormal finding), symptom, or disease temporally associated with the use of a medicinal (investigational) product, whether or not related to the medicinal (investigational) product. (Definition per International Conference on Harmonization [ICH]).

This includes any occurrence that is new in onset or aggravated in severity or frequency from the baseline condition, or abnormal results of diagnostic procedures, including laboratory test abnormalities.

#### **Serious Adverse Event (SAE)**

A serious adverse event as defined by ICH is any untoward medical occurrence that at any dose meets any of the following conditions:

- Results in death
- Is life-threatening (The subject was at risk of death at the time of the event. It does not refer to an event that hypothetically might have caused death if it were more severe.)
- Requires hospitalization or prolongation of existing hospitalization
- Results in persistent or significant disability / incapacity
- Is a congenital anomaly / birth defect

Medical and scientific judgment should be exercised in deciding whether expedited reporting is also appropriate in situations other than those listed above. For example, important medical events may not be immediately life threatening or result in death or hospitalization, but may jeopardize the subject or may require intervention to prevent one of the outcomes listed in the definition above. Any adverse event is considered a serious adverse event if it is associated with clinical signs or symptoms judged by the investigator to have a significant clinical impact.

#### **Unlisted (unexpected) Adverse Event**

The nature or severity of the adverse event is not consistent with the applicable product information. For an investigational product, the expectedness of an adverse event will be determined by whether or not it is listed in the Investigator's Brochure.

#### **Associated with the use of the drug**

An adverse event is considered associated with the use of the drug if the attribution is possible, probable, or very likely by the definitions listed in Section 11.1.2.

#### **Suspected Unexpected Serious Adverse Reactions (SUSAR)**

A SUSAR is a serious adverse drug reaction (SADR), the nature or severity of which is not consistent with the applicable product information.

A serious event or drug reaction is not defined as a SUSAR when:

- it is serious but expected
- it does not fit the definition of a SAE or SADR, whether expected or not

## 11.1.2. Attribution definitions

### Intensity (severity) reporting and attribution

For both serious and non-serious adverse events, the investigator must determine both the intensity of the event and the relationship of the event to study drug administration.

**Intensity** for each adverse event will be determined by using Version 3.0 of the National Cancer Institute Common Toxicity Criteria (NCI CTC) as a guideline, wherever possible. The criteria will be provided to the investigator as a separate document. In those cases where the NCI CTC do not apply, intensity should be defined according to the following criteria:

- mild awareness of sign or symptom, but easily tolerated
- moderate discomfort enough to cause interference with normal daily activities
- severe inability to perform normal daily activities
- life threatening immediate risk of death from the reaction as it occurred
- death

### Relationship to study drug administration will be determined as follows

Not related	An adverse event which is not related to the use of the drug.
Unlikely/doubtful	An adverse event for which an alternative explanation is more likely, e.g., concomitant drug(s), concomitant disease(s), or the relationship in time suggests that a causal relationship is unlikely.
Possible	An adverse event which might be due to the use of the drug. An alternative explanation, e.g., concomitant drug(s), concomitant disease(s), is inconclusive. The relationship in time is reasonable; therefore, the causal relationship cannot be excluded.
Probable	An adverse event which might be due to the use of the drug. The relationship in time is suggestive (e.g., confirmed by dechallenge). An alternative explanation is less likely, e.g. concomitant drug(s), concomitant disease(s).
Definite/very likely	An adverse event which is listed as a possible adverse reaction and cannot be reasonably explained by an alternative explanation, e.g., concomitant drug(s), concomitant disease(s). The relationship in time is very suggestive (e.g. it is confirmed by dechallenge and rechallenge).

## 11.2. Procedures

### 11.2.1. All Adverse Events

All adverse events other than disease progression will be reported from the time a signed and dated informed consent form is obtained until 30 days after the 1st dose of study drug. All events that meet the definition of a serious adverse event will be reported as serious adverse events, regardless of whether they are protocol-specific assessments.

All adverse events, regardless of seriousness, severity, or presumed relationship to study therapy, must be recorded using medical terminology in the source document and the CRF. Whenever possible, diagnoses should be given when signs and symptoms are due to a common etiology (e.g. cough, runny nose, sneezing, sore throat, and head congestion should be reported as "upper respiratory infection"). Investigators must record in the CRF their opinion concerning the relationship of the adverse event to study therapy. All measures required for adverse event management must be recorded in the source document and reported according to sponsor instructions.

All grade 3 and 4 adverse events, considered related, must be followed until resolution of the event, or the event improves to a grade 2 or better. The events of interest in the table above of grade 2 or higher will be followed until grade 1 or better. The unresolved aforementioned events will be followed for a maximum of 6 months.

Sections of the CRFs containing adverse event information will be submitted by the investigator to a representative of the sponsor. Serious adverse event reports will be submitted as described in Section 11.2.2, Serious Adverse Events.

The investigator-Sponsor must report adverse events to the appropriate Independent Ethics Committee/Institutional Review Board (IEC/IRB) that approved the protocol unless otherwise required and documented by the IEC/IRB. The Investigator-Sponsor assumes responsibility for appropriate reporting of adverse events to regulatory authorities. The Investigator-Sponsor shall also report all serious adverse events to the pharmaceutical companies providing the study medication.

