### Adverse Events

Adverse events will be reported by the subject (or, when appropriate, by a caregiver, surrogate, or the subject's legally acceptable representative) for the duration of the study.

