### **Physical Examination**

Any clinically significant abnormalities persisting at the end of the study will be followed by the investigator until resolution or until reaching a clinically stable endpoint.

**Safety and feasibility of treatment:** severe hematological toxicities (grade 3-4) expected.

Grading of toxicity will be defined according to the International Common Toxicity Criteria, version 3.0 (12/12/2003)

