## 11.2.2. Serious Adverse Events and SUSAR

### Reporting of SAE

All serious adverse events occurring during clinical studies must be reported **by fax** to the sponsor IELSG (IELSG Coordinating Center, CH-6500 Bellinzona – Switzerland; Phone: +[contact] – Fax: +[contact]; E-mail: [[contact]](mailto:[contact])) by investigational staff **within 24 hours** of their knowledge of the event, using the **SAE Report Forms**, which must be signed by a member of the investigational staff.

The SAE outcome must be reported within 14 days, using the **SAE Follow up Form**. In case the SAE is still ongoing after 14 days, additional SAE Follow up Forms must be sent again to report the final outcome.

The cause of **death** of a subject in a clinical study, whether or not the event is expected or associated with the investigational agent, is considered a serious adverse event. Any event requiring **hospitalization** (or prolongation of hospitalization) that occurs during the course of a subject's participation in the clinical study must be reported as a serious adverse event, except hospitalizations for:

- a standard procedure for protocol therapy administration
- social reasons in absence of an adverse event
- surgery or procedure planned before entry into the study (must be documented in the CRF)
- study drug administration
- study related procedures defined in the protocol

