## **12.5. Drug accountability**

After patient's registration, the study drug will directly be supplied to the clinical investigator by Mundipharma (see 5. Registration)

The clinical investigator is responsible for ensuring that all study drug (i.e., Depocyt®) received at the site is inventoried and accounted for throughout the study. Study drug must be handled strictly in accordance with the protocol and the container label and will be stored in a limited access area and under locked conditions.

Study drug should be dispensed under the supervision of investigator, a qualified member of the investigational staff, or by a hospital/clinic pharmacist. Study drug will be supplied only to subjects participating in the study. Returned study drug must not be dispensed again, even to the same subject. Study drug may not be relabeled or reassigned for use by other subjects. The investigator agrees neither to dispense the study drug form, nor store it at any site other than study sites agreed upon the sponsor.

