### Timing of treatment and investigations

	PRE-TREATMENT PHASE	TREATMENT PHASE						CONSOLIDATION PHASE						FOLLOW UP PHASE	
		I	II	III	INTERIM RESTAGING	IV	V	VI						POST THERAPY RESTAGING	MINIMAL EVALUATION
DAY	-28	0	21	42		63	84	105	126	140	150	165			
COURSES		1	2	3		4	5	6							
CHOP		X	X	X		X	X	X							
RITUXIMAB		X	X	X		X	X	X							
IT CHEMOTHERAPY			X	X		X	X								
METHOTREXATE									X	X					
RADIOTHERAPY												X			
History, physical examination		X	X	X	X	X	X	X	X	X	X		X	X	X
Orchiectomy (1)		X													
Testicular ultrasound		X				X							X		X
CT chest, abdomen		X				X							X		X
CT-PET (2)		X											X		
Blood counts + differential		X	X	X	X	X	X	X	X	X	X		X	X	X
Bone marrow aspirate+biopsy (3)		X													
Lumbar puncture (4)		X													
$\beta$ 2-microglobulin IgA, IgG, IgM		X											X		X
HIV, HBV, HCV (5)		X													
Biochemistry (6)		X							X	X	X		X		X
Biochemistry (7)			X	X	X	X	X	X						X	
MUGA or cardiac echo		X													

- (1) Orchiectomy should be performed within 2 months before study entry
- (2) CT-PET mandatory only at final evaluation
- (3) Bone marrow mandatory at baseline. Will be repeated only if clinically indicated
- (4) Lumbar Puncture for determination of cell count, differential, cytologic and cytoflussimetry examination of CNS liquor
- (5) Patients HCV+ with no signs of active chronic hepatitis histologically confirmed: HCV-RNA once a month; Patients HBcAb +, HbsAg -, HBs Ab+/- with HBV-DNA negative: HbsAg once a month
- (6) Biochemistry including serum Creatinine, clearance Creatinine AST, ALT, ALP, total Bilirubin, albumin, LDH
- (7) Biochemistry comprises: AST, ALT, ALP, LDH, Creatinine, total bilirubin, albumin

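### Section 11.2.1 closes adverse-event reporting 30 days after the first dose, contradicting 9.1.1 and 9.4; read literally, it omits both methotrexate courses and at least half of R-CHOP

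*Combined protocol and SAP*

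**What the plan says.** The protocol gives three end points for collecting adverse events.

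- **Section 11.2.1 (All Adverse Events)**, the reporting procedure, has all adverse events other than progression reported from the time consent "is obtained until 30 days after the 1st dose of study drug".
- **Section 9.1.1 (Overview)**: "All subjects will be monitored for adverse events throughout the study and for 30 days after the end of treatment".
- **Section 9.4 (Safety evaluations, Adverse Events)** has events reported by the subject, a caregiver or a "legally acceptable representative) for the duration of the study".

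The last two differ on how long collection continues after treatment, but both cover every treatment component. The first does not.

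Four other places bear on the reading. The second paragraph of 11.2.1 requires every adverse event to be entered in the source document and CRF, and sets no period of its own. Section 11.2.2 deals with serious events separately: "All serious adverse events occurring during clinical studies must be reported", with no 30-day limit. Section 12.5 glosses the term study drug: "The clinical investigator is responsible for ensuring that all study drug (i.e., Depocyt®) received at the site". Section 2.1 makes safety and feasibility of the whole programme the primary objective, and 9.4 lists under that heading "severe hematological toxicities (grade 3-4) expected".

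**The concern.** The sentence in 11.2.1 sets the reporting period, so it is where a site would look for the rule. It ties the period to the start of treatment, although treatment lasts more than five months. The protocol does not say which of the three statements prevails.

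The primary objective rests on toxicity data. The components added to R-CHOP to protect the CNS are intrathecal liposomal cytarabine and systemic methotrexate. A window that closes after the first dose would include no methotrexate exposure and at most half of the intrathecal doses. If some sites followed 11.2.1 and others followed 9.1.1 or 9.4, toxicity counts in about 35 patients could be too low overall and not comparable between sites.

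The events at risk are the non-serious ones. An uncomplicated grade 3-4 cytopenia found on a blood count need not meet the seriousness definition in 11.1.1, yet 9.4 names that kind of toxicity under safety and feasibility.

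**Working it through.** The plan gives no figure to reproduce. The check is day arithmetic on the schedule.

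**Inputs**

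- Attachment 9: R-CHOP on days 0, 21, 42, 63, 84 and 105; DepoCyt in cycles 2 to 5, so days 21, 42, 63 and 84; methotrexate on days 126 and 140.
- Radiotherapy start: day 154 from Section 3.2 (140 + 14), or day 165 from Attachment 9. The three weeks in Section 7 give 140 + 21 = 161, which lies between them.
- Radiotherapy length: Section 7 allows 10 to 20 fractions. Assuming five per week, these span 11 to 25 days.
- End of treatment: 154 + 11 = day 165 at the earliest, 165 + 25 = day 190 at the latest. The synopsis start of week 24 (24 × 7 = day 168) would add three days and does not change the picture.

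**Where the printed window closes** (day of first dose + 30)

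- Study drug read as R-CHOP: 0 + 30 = day 30.
- Study drug read as DepoCyt: 21 + 30 = day 51.

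**Treatment given after it closes**

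| Component | After day 30 | After day 51 |
|---|---|---|
| R-CHOP | 4 of 6 (days 42, 63, 84, 105) | 3 of 6 (days 63, 84, 105) |
| DepoCyt | 3 of 4 (days 42, 63, 84) | 2 of 4 (days 63, 84) |
| Methotrexate | 2 of 2 | 2 of 2 |
| End-of-treatment radiotherapy | all | all |

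**Share of treatment days outside the window** ((end − close) / end)

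| End of treatment | Close at day 30 | Close at day 51 |
|---|---|---|
| Day 165 | 135/165 = 81.8% | 114/165 = 69.1% |
| Day 190 | 160/190 = 84.2% | 139/190 = 73.2% |
| Day 140 (radiotherapy concurrent with R-CHOP) | 110/140 = 78.6% | 89/140 = 63.6% |

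**Would changing 1st to last be enough?**

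- Study drug as DepoCyt: 84 + 30 = day 114, before both methotrexate courses.
- Study drug as R-CHOP: 105 + 30 = day 135, after the first methotrexate course and before the second.

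**Under 9.1.1**, collection runs at least to 165 + 30 = day 195, or 190 + 30 = day 220, and covers every component.

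**The case against.** The strongest reply is that this is a one-word slip with little practical effect. Two other sections give the longer period. The follow-up of related grade 3-4 events in 11.2.1, for up to six months if unresolved, fits poorly with a day 30 cut-off. The second paragraph of 11.2.1 orders CRF recording of all events with no period attached, and the adverse-event pages then go to the sponsor. Serious events have their own rule. Blood counts are scheduled before every R-CHOP and methotrexate course, at restaging and at follow-up visits, and 9.1.1 requires haematology results to be reviewed for toxicity. Section 14.1 mentions CRF completion guidelines that could settle the period; they are not among the documents.

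Most of this stands, and it limits the consequence. A reader might infer that non-serious events from most of the course would go unrecorded. The documents do not support that. Loss occurs only at a site that lets the first sentence of 11.2.1 govern the second paragraph and sets aside 9.1.1 and 9.4. What remains is that the recording paragraph directly follows the sentence setting the period, so that reading is open to a site. Counts taken before each course can also miss the nadir.

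A reader might also infer that the protocol defines study drug as DepoCyt throughout. It does not. Section 12.5 concerns accountability for the supplied product, Section 12 also covers rituximab, and 9.1.2 uses the first dose of study drug in a way that fits R-CHOP on day 0. The day 51 and day 114 figures are therefore one possible reading. The ambiguity is still a reason not to use that term for the end point.

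**Conclusion.** The contradiction is real and the sentence in 11.2.1 is wrong as written. Read literally, it ends reporting at about day 30 (day 51 on the DepoCyt reading). It omits 3 to 4 of 6 R-CHOP cycles, 2 to 3 of 4 DepoCyt doses, both methotrexate courses and end-of-treatment radiotherapy. That is 69-84% of treatment days, or 64-79% if radiotherapy is concurrent. These shares depend on the nominal Attachment 9 calendar without delays and, for the first range, on five radiotherapy fractions per week.

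The shares describe the reporting window, not lost data. The number of events missed cannot be estimated from the documents, and nothing shows that any site applied the sentence literally. Under-reporting of non-serious toxicity is possible, not certain, and reporting of serious events is not affected.

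A reader might extend the point to hepatitis monitoring, since the monthly tests in footnote 5 of Attachment 9 have no stop date. That is a separate scheduling detail. The footnote already orders the tests, liver chemistry is scheduled at the study visits, and the reporting window does not govern either.

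Severity is minor: a probable drafting slip, but in the rule that feeds the primary objective.

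**What to change.** In 11.2.1, replace the end point with: *until 30 days after the end of all protocol treatment, including methotrexate and radiotherapy*. This is consistent with 9.1.1. A cross-reference to 9.1.1 and 9.4 would make clear that one rule applies.

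Do not write last dose of study drug. Because of the usage in 12.5, that could still close reporting at about day 114, before methotrexate.

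The cost is one corrected sentence and slightly more adverse-event recording at any site that now follows 11.2.1 literally. No visit or test is added.
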